### Statistical Analysis Plan

Regeneron Pharmaceuticals Inc. / Protocol: CMP-001-010 IQVIA Biotech (Confidential) Project # RZA44091

otherwise, these displays are summary tables that summarize data for the corresponding analysis set:

- Subject information
  - Demographics
  - Baseline characteristics
  - Disposition
  - Medical history
  - Cancer history
  - o ECOG
- Efficacy
  - o ORR, DOR, TTR, PFS per RECIST v1.1 by BICR and Investigator
  - o OS
  - Selected subgroup analysis
- Safety
  - o Study drug exposure: CMP-001 and nivolumab
  - o Prior and concomitant medications
  - Prior and concomitant procedures
  - o All TEAEs (SAE, AESI)
  - o Summary of clinical laboratory results
  - o Summary of ECG results

### H. Test Sizes

Not Applicable.

### I. Multiple Comparisons

No control for the effect of multiple comparisons is planned.

### J. Analysis Sets

Five analysis sets will be defined for use with various analyses, provided that there are data available for the analysis set to be defined and analysis to be performed. The following table illustrates the relationship between each population and the analyses for which the data from the population will be used.

Regeneron Pharmaceuticals Inc. / Protocol: CMP-001-010 IQVIA Biotech (Confidential) Project # RZA44091

	Analysis						
Analysis Set	Baseline	Subject Disposition	Efficacy	Safety	PD	Immuno genicity	Tumor Biopsy
Intent-to-Treat	X	X	X				
Safety				X			
Per Protocol			X*				
Pharmacodynamic					X		X
Immunogenicity						X	

\* The efficacy analyses may also be performed for the Per Protocol Analysis Set if deemed appropriate.

### 1. Intent-to-Treat Analysis Set

The Intent-to-Treat (ITT) Analysis Set is defined as all subjects who receive at least 1 (partial or full) dose of study treatment.

### 2. Safety Analysis Set

The Safety Analysis Set is defined as all subjects who receive at least 1 dose of study treatment.

### 3. Per Protocol Analysis Set

The Per Protocol Analysis Set is defined as all subjects who receive at least 1 dose of study treatment and are without major protocol deviations.

### 4. Pharmacodynamic Analysis Set

The Pharmacodynamic Analysis Set is defined as all subjects who receive at least 1 dose of CMP-001 and have at least 1 measurable sample at Baseline and at least 1 evaluable biomarker sample after CMP-001 administration.

### 5. Immunogenicity Analysis Set

The Immunogenicity Analysis Set is defined as all subjects who receive at least 1 dose of CMP-001 and have at least 1 non-missing ADA result after CMP-001 administration.

### K. Subgroups of Analysis Populations

Not applicable.

### L. Data Display Characteristics

### Statistical Analysis Plan

Regeneron Pharmaceuticals Inc. / Protocol: CMP-001-010 IQVIA Biotech (Confidential) Project # RZA44091

Data displays produced for this study will include three types—summary tables, data listings, and figures. Unless stated otherwise, data listings will be produced for all subjects. Summary tables will be produced as specified in following sections. Additional data listings will be produced for outcome measures that involve extensive procedures to derive the analyzed outcomes such as efficacy measures. Figures will be produced when specified in sections to follow.

Data listings will simply list the data recorded on the CRF or derived for each subject. They will be ordered by site, subject number, and time of assessment (i.e., visit). When expedient, additional levels of ordering hierarchy may reflect subsets of assessments within subject.

The summary statistics displayed will be a function of the type of data associated with the summarized assessment. Unless stated otherwise in relevant sections to follow, continuous data will be summarized with the number of non-missing values, mean, standard deviation, minimum, median, and maximum. Categorical data will be summarized as the number of subjects within each category (with a category for missing data, if applicable). Percentages of subjects within each of the possible categories will be calculated from the number of subjects in the corresponding analysis population, unless stated otherwise. Some continuous variables may also be grouped into categorical levels and evaluated in frequency tables.

Summary tables, listings and figures will include a "footer" of explanatory notes that will indicate, at a minimum, the following:

- Program source (e.g., SAS program name)
- Database extraction date (e.g., database lock date or data cut date or data extract date)
- SAS output generation date and time

The purpose of the database extraction date is to link the output to a specific database cut, either active or locked database, that is write-protected for replication and future reference. Individual data listings will display all the relative values supporting corresponding table and figures.

### M. Blinded Review of Data

Blinded Independent Central Review (BICR) RECIST v1.1 assessment will be used for the primary efficacy assessments of tumor response. A detailed charter for the BICR will be created prior to the first BICR assessment.

## Statistical Analysis Plan

Regeneron Pharmaceuticals Inc. / Protocol: CMP-001-010 IQVIA Biotech (Confidential) Project # RZA44091

Blinded Independent Central Review responsibilities also include confirmation of disease progression prior to study entry, in addition to the primary efficacy assessment of the study.

## VII. Subject Accountability

### A. Subject Characteristics

Demography and Baseline Characteristics. Data collected about the following subject characteristics at the screening visit will be summarized:

- Age
  - Age will be calculated as the number of years elapsed between birth date and the date of the ICF date, adjusted for whether the birthday has passed as of the day of the screening visit. (This corresponds to the typical calculation of age a person would use in conversation.)
- Sex
  - o Childbearing potential yes/no
  - Non-childbearing potential, and confirmation by site
- Race
- Ethnicity
- Height
- Baseline Weight
- Baseline Body Mass Index

All demography data including informed consent date will be listed.

Baseline Disease Characteristics. Time since Initial Diagnosis of Primary Cancer to First Dose (Months), Disease Type at Enrollment, Tumor Burden at Baseline, Measurable Disease at Baseline, Baseline ECOG, and other key baseline information will be summarized for ITT Analysis Set and presented in a listing.

Medical History Other Than Melanoma Cancer. Medical history including CNS screening will be summarized in a table and listed by subject. Medical history will be coded using MedDRA, associating lower-level terms with preferred terms and system organ classes by the primary hierarchy.

Melanoma Cancer History. Listings of all collected data related to Melanoma history will be provided for ITT Analysis Set. A summary of the following elements will also be provided:

• PD-L1 status

### Statistical Analysis Plan

Regeneron Pharmaceuticals Inc. / Protocol: CMP-001-010 IQVIA Biotech (Confidential) Project # RZA44091

- Clinical staging
  - Clinical staging at diagnosis
  - Tumor status
  - Nodal status
  - Metastatic disease status
- Pathologic staging
  - Pathologic staging at diagnosis
  - Tumor status
  - Nodal status
  - Metastatic disease status

Prior Primary Cancer Treatments. Listings of key data related to prior melanoma treatments will be provided for ITT Analysis Set, and include the following information:

- Number of Lines of Prior Systemic Therapies: summarized categorically  $(1, 2, \ge 3)$
- Any Prior Therapy
  - o Prior Systemic Therapy
  - o Prior Radiotherapy
  - o Prior Cancer-related Surgery
- Reason for Discontinuation from Any Prior Systemic Therapy
- Regimen Best Response on Any Prior Systemic Therapy
- Duration of Exposure to Any Prior Systemic Therapy (months), summarized continuously
- Administrative Setting of Prior Systemic Therapy
- Time since Completion of Prior Adjuvant Systemic Therapy to First Dose Date (< 6 months; ≥ 6 months)

All prior melanoma treatments will be captured in the EDC separately from other prior medications. Combination treatments should be considered as a single regimen and recorded as such in the EDC. Details regarding all prior melanoma treatments, including drug generic name, start date, end date, regimen best response to prior therapy, and administrative setting, as well as key data related to prior melanoma treatments, will be listed by subject for ITT Analysis Set.

Data on Prior Cancer Radiation and Prior Cancer Surgery will be captured on different pages of eCRF and presented in separate by-subject data listings.

### Statistical Analysis Plan

Regeneron Pharmaceuticals Inc. / Protocol: CMP-001-010 IQVIA Biotech (Confidential) Project # RZA44091

### **B.** Disposition

As of the data cutoff date, the number and percentage of subjects who screen fail and enroll in the study (receive at least one dose of study treatment), discontinue study treatment, and discontinue the study will be summarized. The primary reason for treatment(s) and study discontinuation and follow-up status will also be summarized for the ITT Analysis Set.

Study treatment (CMP-001 only or both CMP-001 and Nivolumab) may be discontinued for any of the following occurrences:

- Adverse Event
- PD per RECIST v1.1
- Subject Achieved and Maintained a Confirmed CR or iCR (and has been treated for at least 48 weeks, and has received at least 3 doses of both study treatments beyond the date of initial CR/iCR)
- Upon Request of the Sponsor or Regulatory Agency
- Clinical Disease Progression
- Medically Necessary in the Opinion of the Investigator
- Subject Withdrew Consent for Treatment
- Subject Became Pregnant or Began Breastfeeding
- Subject Lost to Follow-up
- Death
- Subject Completed 2 Years of Study Treatment
- End of Clinical Trial
- Other

Study Participation may be discontinued for any of the following occurrences:

- Completed
- Adverse Event
- Subject Withdrew Consent
- Lost to Follow-Up
- Death
- Study Terminated by Sponsor
- End of Clinical Trial
- Other

Percentages of subjects who withdrew for each of these reasons will be calculated using all members of the relevant analysis set for the denominator.

Time on Study (TOS) will be summarized descriptively. For subjects who are still on study as of the data cutoff date, TOS will be calculated as follows:

TOS (months) = (Data Cutoff Date – First Dose Date + 1) / 30.4375

## Statistical Analysis Plan

Regeneron Pharmaceuticals Inc. / Protocol: CMP-001-010 IQVIA Biotech (Confidential) Project # RZA44091

As for subjects who exited the study on or prior to the data cutoff date, TOS will be calculated as:

TOS (months) = (Study End Date – First Dose Date + 1) / 30.4375

Subject disposition will be presented in a by-subject data listing.

### C. Protocol Deviations and Population Inclusions

All protocol deviations will be captured electronically outside of the Electronic Data Capture (EDC) system in the IQVIA Biotech IL-2 system and presented in a by-subject data listing. All deviations will be reviewed on an ongoing basis and classified as major or minor.

## VIII. Efficacy Analyses

The primary efficacy analyses will use data from the ITT population. Analyses of data from the Per-protocol population may accompany ITT population analyses if substantial number of ITT population subjects are excluded from the Per-protocol population.

### A. Efficacy Endpoints

Confirmed Objective Response Rate (ORR)

The confirmed ORR is defined as the proportion of subjects in the analysis set who have confirmed best response as CR or PR per RECIST v1.1 as assessed by BICR.

The confirmed ORR will be calculated as the number of subjects with a confirmed CR or PR divided by the number of subjects in the analysis population [ORR = (confirmed CR + confirmed PR)/number of subjects] for the ITT Analysis Set. 95% Clopper-Pearson CIs for the ORR will be calculated.

Subjects who discontinue due to death as a result of disease progression, or disease progression, prior to having a post-Baseline tumor assessment will be classified as having a best response of PD. Subjects who discontinue prior to having a post-Baseline scan for other reasons will be counted as non-responders in the ITT analyses. Objective Response assessment evaluated after new anti-cancer treatment will not be considered for BOR calculation.

Confirmed Best Overall Response (BOR)

## Statistical Analysis Plan

Regeneron Pharmaceuticals Inc. / Protocol: CMP-001-010 IQVIA Biotech (Confidential) Project # RZA44091

The Best Overall Response for a subject is the best response designation as assessed by BICR, recorded between the date of the first dose of study treatment and the date of objectively documented progression per RECIST v1.1, or the date of treatment discontinuation, whichever occurs first.

Per RECIST v1.1, CR or PR must be confirmed by a confirmatory response assessment performed at least 4 weeks after the initial response. Objective Response assessment evaluated after new anti-cancer treatment will not be considered for BOR calculation.

BOR will be derived as below:

Disease Control Rate (DCR)

The confirmed disease control rate is defined as the proportion of subjects in the analysis set who have a confirmed Best Overall Response of CR, PR, or stable disease (SD) per RECIST v1.1 by BICR.

Per RECIST v1.1, CR or PR must be confirmed by a confirmatory assessment performed at least 4 weeks after the initial response. In the case of SD, measurements must have met the SD criteria at least once after study entry at a minimum interval of 6 weeks. OR assessment evaluated after new anti-cancer treatment will not be considered for DCR calculation.

Treatment Effect in Non-injected Target Lesions

The treatment effect in non-injected target lesions will be assessed separately from the overall effect. The confirmed ORR in non-injected target lesions based on the RECIST v1.1 per BICR measurements will be derived using the same approach as ORR.

Data for the injected target and non-injected target lesions will be analyzed as a secondary efficacy analysis using the following definitions (Goldmacher, 2020).

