APPENDIX D. RESPONSE EVALUATION CRITERIA IN SOLID TUMORS (RECIST) VERSION 1.1

Response criteria were adapted from: RECIST Criteria; Version 1.1, 2009 (https://project.eortc.org/recist/wp-content/uploads/sites/4/2015/03/RECISTGuidelines.pdf) These criteria are provided as reference; any discrepancy should be resolved by consulting the original publication.

Assessment of Overall Tumor Burden and Measurable Disease

To assess objective response, it is necessary to estimate the overall tumor burden at Baseline and use this as a comparator for subsequent measurements. Only subjects with measurable disease at Baseline should be included in protocols where objective tumor response is an endpoint. Measurable disease is defined by the presence of at least 1 measurable lesion.

A measurable lesion is defined as one that can be accurately measured in at least 1 dimension (longest diameter in the plane of measurement is to be recorded) with a minimum size of:

- 1 cm by CT scan (CT scan slice thickness no greater than 0.5 cm)
- 1 cm caliper measurement by clinical examination (lesions which cannot be accurately measured with calipers should be recorded as non-measurable)
- 2 cm by chest X-ray

Non-measurable lesions are defined as all other lesions, including small lesions (longest diameter < 1.0 cm or pathological lymph nodes with \geq 10 to < 1.5 cm short axis) as well as truly non-measurable lesions. Lesions considered truly non-measurable include: leptomeningeal disease, ascites, pleural or pericardial effusion, inflammatory breast disease, lymphangitic involvement of skin or lung, and abdominal masses/abdominal organomegaly identified by physical examination that is not measurable by reproducible imaging techniques.

Special Considerations Regarding Lesion Measurability:

Bone lesions:

Bone scan, PET scan, or plain films are not considered adequate imaging techniques to measure bone lesions. However, these techniques can be used to confirm the presence or disappearance of bone lesions. Lytic bone lesions or mixed lytic-blastic lesions, with identifiable soft tissue components, that can be evaluated by cross-sectional imaging techniques such as contrast-enhanced CT or MRI can be conserved as measurable lesions if the soft tissue component meets the definition of measurability described above. Blastic bone lesions are non-measurable.

Cystic lesions:

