All other lesions (or sites of disease) including pathological lymph nodes should be identified as non-target lesions and should also be recorded at Baseline. Measurements are not required, and these lesions should be followed as 'present,' 'absent,' or in rare cases 'unequivocal progression.' In addition, it is possible to record multiple non-target lesions involving the same organ as a single item on the case record form (ie, 'multiple enlarged pelvic lymph nodes' or 'multiple liver metastases').

Tumor Response Criteria

Evaluation of Target Lesions

Complete response: Disappearance of all target lesions. Any pathological lymph nodes (whether target or non-target) must have reduction in short axis to < 1 cm.

Partial response: At least a 30% decrease in the sum of diameters of target lesions, taking as reference the Baseline sum diameters.

Progressive disease: At least a 20% increase in the sum of diameters of target lesions, taking as reference the smallest sum on study (this includes the Baseline sum if that is the smallest on study). In addition to the relative increase of 20%, the sum must also demonstrate an absolute increase of at least 0.5 cm (NOTE: the appearance of 1 or more new lesions is also considered progression).

Stable disease: Neither sufficient shrinkage to qualify for PR nor sufficient increase to qualify for PD, taking as reference the smallest sum diameters while on study.

Evaluation of Non-Target Lesions

Complete response: Disappearance of all non-target lesions and normalization of tumor marker level. All lymph nodes must be non-pathological in size (< 1 cm short axis).

Non-complete response/Non-progressive disease: Persistence of 1 or more non-target lesion(s) and/or maintenance of tumor marker level above the normal limits.

Progressive disease: Unequivocal progression of existing non-target lesions (NOTE: the appearance of 1 or more new lesions is also considered progression).

Evaluation of Best Overall Response

The best overall response (BOR) is recorded from the start of the study treatment until the End of Clinical Trial, taking into account any requirement for confirmation. The subject's BOR assignment will depend on the findings of both target and non-target disease and will also take into consideration the appearance of new lesions. In non-randomized studies where response is the primary endpoint, confirmation of PR or CR is needed to deem either one the 'BOR.'

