Disease status will be assessed by computed tomography (CT) or magnetic resonance imaging (MRI) and other appropriate measures beginning predose at Week 13 Day 1 (W13D1) and repeated every 9 weeks (eg, W22D1) while the subject is on treatment. All scans should be performed at least 2 weeks after the previous CMP-001 IT injection to prevent injection-related pseudoprogression. Imaging should not be delayed for delays in treatment. Disease assessments may continue every 12 weeks for subjects with a response lasting more than 1 year.

Responses (CR, PR, immune complete response [iCR], or immune partial response [iPR]) will be confirmed by a follow-up disease assessment performed at least 4 weeks after the initial response date, and at least 2 weeks after the last CMP-001 injection.

Subjects who discontinue study treatment should complete an end of treatment (EOT) visit and 100-day safety follow-up. Subjects who have stopped all study treatment but have not met criteria for study discontinuation should remain on study for post-treatment follow-up (PTFU) and long-term survival follow-up (LTSFU) and receive study evaluations for efficacy according to the Schedule of Assessments.

Note: 100DFU = 100-Day Follow-up; EOT = End of Treatment; IT = intratumoral; IV = intravenous; LTSFU = long-term survival follow-up; PTFU = posttreatment follow-up; Q3W = every 3 weeks; Q9W = every 9 weeks; Q12W = every 12 weeks; QW = every week.

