### Duration of Response (DOR)

Duration of response will be based on RECIST v1.1 as determined by BICR and calculated for confirmed responders of the ITT Analysis Set. The DOR will be measured from the time at which criteria are first met for CR or PR (whichever is first recorded) until the first date that recurrence or PD is objectively documented (taking as reference for PD the smallest measurements recorded on study).

DOR is only defined for subjects who have a confirmed BOR of CR or PR. Per the BOR definition, subjects with an overall response of CR or PR must have a repeat tumor assessment performed no less than 4 weeks after the criteria for response are first met. The first date at which a CR or PR response was noted will be used to calculate DOR, not the date of the confirmatory tumor assessment. Subjects who do not have PD or death will be censored at the date of their last disease assessment. For subjects who started a subsequent anti-cancer therapy before having a documented PD, the last disease assessment prior to the start of the

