## Statistical Analysis Plan

Regeneron Pharmaceuticals Inc. / Protocol: CMP-001-010 IQVIA Biotech (Confidential) Project # RZA44091

subsequent therapy will be used. Details of the censoring rules are provided in Table 1a.

DOR will be calculated as follows:

DOR (months) = (Event/Censoring Date – Response Start Date + 1) / 30.4375

Progression-Free Survival (PFS)

Progression-free survival is defined as the time from first dose of study treatment to the date of documented PD based on RECIST v1.1 by BICR or death from any cause, whichever occurs first. Subjects who are alive and progression-free at the time of analyses will be censored in the analyses at the date of their last disease assessment. For subjects who started a subsequent anti-cancer therapy before having a documented PD, the overall response assessment evaluated after new anti-cancer treatment will not be considered for PFS calculation, and the last disease assessment prior to the start of the subsequent therapy will be used. Details of the censoring rules are provided in Table 1a.

PFS will be calculated as follows:

PFS (months) = (Event or Censoring Date – First Dose Date + 1) / 30.4375

All events of RECIST v1.1 disease progression or death will be counted regardless of whether the event occurred while the subject was on study drug or had previously discontinued treatment. Subjects who do not experience disease progression or death before the analysis cutoff date will be censored at the date of last adequate tumor assessment. Date of censoring for these subjects will be based on the last tumor assessment prior to missing the assessments. Censoring rules are summarized in Table 1a. If a subject meets the criteria for more than 1 censoring rule, PFS will be censored at the earliest censoring date.

Secondary Efficacy Assessments by Investigator

The secondary efficacy endpoints of ORR, BOR, DCR, DOR and PFS by investigator assessments will be derived using the same approach as above.

Overall Survival (OS)

Overall survival will be calculated as the time from first dose of study treatment to the date of death due to any cause. Subjects who are alive or lost to follow-up at the time of the analysis data cutoff will be censored at the time of last known alive date, or at data cutoff date, whichever occurs first. Censoring rules are detailed in Table 1c, and the last contact date will be derived as shown in Table 2.

OS will be calculated as follows:

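### Read literally, the SAP ends the BICR best-overall-response window at treatment discontinuation, so a response first documented afterwards would not count toward the primary confirmed ORR

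*SAP*

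**What the plan says.** SAP Section VIII.A defines confirmed ORR as the share of the ITT set with a confirmed best response of CR or PR by BICR. Under Confirmed Best Overall Response, the same section opens the window at first dose and closes it at "the date of objectively documented progression per RECIST v1.1, or the date of treatment discontinuation, whichever occurs first". It adds a second cut-off: "Objective Response assessment evaluated after new anti-cancer treatment will not be considered for BOR calculation". A derivation is announced next, but in the text available the next item is the disease control rate.

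Other places bear on the window:

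- SAP Section II.A keeps subjects who have stopped treatment on study for follow-up, to "and receive study evaluations for efficacy according to the Schedule of Assessments".
- Protocol Table 1 schedules disease assessment at the end-of-treatment (EOT) visit and in posttreatment follow-up. Footnote a places EOT assessments within 7 days after discontinuation. Footnote c and Sections 4.5 and 7.8 give posttreatment scans every 3 months to subjects who stopped for reasons other than progression.
- Protocol Appendix D says that BOR "is recorded from the start of the study treatment until the End of Clinical Trial". Its introduction adds: "These criteria are provided as reference; any discrepancy should be resolved by consulting the original publication".
- The SAP's PFS text counts events "regardless of whether the event occurred while the subject was on study drug or had previously discontinued treatment".
- SAP Section I.B gives the SAP precedence over the protocol.

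**The concern.** Under the literal rule a subject can stop treatment without progression, start no other therapy, have a first PR on a planned off-treatment scan, have it confirmed, and still be a non-responder in the primary analysis. With the ITT denominator fixed, dropping later assessments can only lower the confirmed ORR or leave it unchanged.

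The window carries into other results. Disease control rate and the non-injected-lesion ORR use the same approach. For the Investigator analyses: "The secondary efficacy endpoints of ORR, BOR, DCR, DOR and PFS by investigator assessments will be derived using the same approach as above". An affected responder also leaves the duration-of-response set, since "DOR is only defined for subjects who have a confirmed BOR of CR or PR".

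Two gaps make the derivation hard to reproduce. The text does not say whether a scan after discontinuation may confirm a response first seen on treatment. Nor does it say which date closes the window when CMP-001 and nivolumab stop on different days.

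**Working it through.** **1. Method check.** The plan gives no figure for the effect of the window. Protocol Section 9.1 does give a Clopper-Pearson interval, 12.7% to 29.2% for an ORR of 20% with 100 subjects. With x responders of n, the lower limit is the 0.025 quantile of Beta(x, n − x + 1) and the upper limit is the 0.975 quantile of Beta(x + 1, n − x). For x = 20 and n = 100 this gives 12.67% to 29.18%, which reproduces the plan.

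**2. Which scans fall outside.** An EOT scan dated on or before discontinuation still counts. One dated in the following 7 days does not, and neither does any posttreatment scan. On-treatment scans are sparse: the first is at Week 13 and the next at Week 22. A subject with stable disease at Week 13 who stops for toxicity before Week 22 may have the next scan only after the window has closed.

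**3. Who can be affected.** Subjects with BICR progression are already closed out. Subjects who stop before any post-Baseline scan are already classified as progressors or non-responders by Protocol 9.5.1 and the SAP's ORR text, so they are not lost through this rule. A response first seen at EOT needs a further scan at least 4 weeks later, and only subjects who stopped for reasons other than progression have one scheduled. What remains is mainly subjects who stopped for such reasons, had no earlier response, and then responded and were confirmed without progression or new therapy.

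**4. Confirmation.** Hypothetical case: a PR is first seen at Week 22 and treatment stops at Week 24. The earliest confirmation is Week 22 + 4 = Week 26, which is after discontinuation. The visible text does not say whether it counts.

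**5. Closing date.** The documents offer several candidates:

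- Protocol Table 1 footnote a dates removal from CMP-001 to the Investigator's decision.
- Protocol 4.5 defines discontinuation as stopping with no restart within 12 weeks.
- Protocol 5.1.1 allows nivolumab to continue after CMP-001 stops, and SAP VII.B covers stopping CMP-001 alone or both drugs.
- SAP IX.A.1 uses a discontinuation or completion date distinct from last dose.
- SAP Table 2 lists an EOT eCRF date.

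The BOR definition names none of these.

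**6. Size.** SAP II.C gives n = 44. One responder is 100/44 = 2.27 points. The documents do not give the number of responders or how many are affected. As an assumption, take 9 responders, since the design alternative of 20% gives 0.20 × 44 = 8.8:

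| Affected | Counted | ORR | 95% CI |
|---|---|---|---|
| 0 | 9/44 | 20.5% | 9.8 to 35.3 |
| 1 | 8/44 | 18.2% | 8.2 to 32.7 |
| 2 | 7/44 | 15.9% | 6.6 to 30.1 |

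The intervals are 23 to 26 points wide, so each shift is small against the sampling uncertainty.

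**The case against.** The strongest reply is that an on-treatment response window is a legitimate choice, and that the operative derivation has not been seen. Protocol Appendix E ends the iRECIST BOR at the end of treatment, Protocol 9.5.1 sets no end to the window, Appendix D is reference text, and SAP I.B allows departures from the protocol. This stands to the extent that the rule should not be called a protocol violation. The unseen derivation limits confidence. The corresponding immune-BOR derivation in the SAP is only a ranking of categories, so the missing text may or may not help.

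A reader might infer that the new-therapy cut-off is redundant. Protocol 4.4 bars other systemic anticancer therapy during the study, so new therapy would ordinarily follow discontinuation and the two rules sit poorly together. However, SAP Table 1b has a row for subjects who continue study treatment after unconfirmed progression and then start new therapy, so the cut-off may still do some work.

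A reader might also see a contradiction with PFS, which counts off-treatment events. PFS is a different endpoint, and follow-up scans are needed for PFS and duration of response in any case. Both points support the reading but do not prove it.

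The rule is also conservative for a single-arm study. That is true, but a conservative rule still needs one reproducible definition.

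**Conclusion.** The point holds as a should-fix item with medium confidence. The visible SAP text closes the primary endpoint's response window at discontinuation, and nothing visible reopens it for planned EOT or posttreatment scans. The confirmation rule and the closing date are unsettled.

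The effect is 2.3 points per affected responder at N = 44. It is never upward, and the number affected may be zero. The 9-responder base is an assumption. The conclusion also depends on the unseen derivation text not changing the rule.

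Two stronger readings are not supported. One is that the rule materially understates the ORR: the documents give no count of responses first seen off treatment, and the eligible group is narrow. The other is that it could reverse a finding against the 7% reference rate. The lower limit does pass below 7% at 7 of 44 in the illustration, but SAP Sections II.C and VIII.B make the analyses exploratory, so a reported estimate is at stake rather than a formal decision.

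**What to change.** In SAP Section VIII.A:

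- Define BOR as the best BICR response from first dose to the earliest of RECIST v1.1 progression, start of new anticancer therapy, or data cutoff.
- State that EOT, unscheduled and posttreatment scans inside that window count for both initial response and confirmation.
- Align the ORR sentence on subjects who stop before a post-Baseline scan, so that it applies only to those with no such scan inside the window.
- If an on-treatment-only ORR is kept, report it as a sensitivity analysis and name its closing date, including when the two drugs stop on different days. The EOT eCRF date in Table 2 is one candidate.

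The cost is a few SAP sentences and one derivation change. No new data are needed, because the scans are already scheduled and sent to BICR. The downside is that the estimate can only rise or stay the same, and the change comes after enrollment closed in an open-label study. Showing both versions keeps it transparent.
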